6.5. Statistical Software

All statistical analyses will be performed using SAS[®] Version 8.2 or higher.

SAFETY AND ADVERSE EVENT REPORTING

6.6. Definitions

An **Adverse Event (AE)** is defined as any new untoward medical occurrence or worsening of a pre-existing medical condition in a patient or clinical investigation subject administered an investigational (medicinal) product and that does not necessarily have a causal relationship with this treatment. An AE can therefore be any unfavorable and unintended sign (including an abnormal laboratory finding, for example), symptom, or disease temporally associated with the use of investigational product, whether or not considered related to the investigational product. A laboratory abnormality is considered an adverse event if it results in discontinuation from the study drugs, necessitates therapeutic medical intervention, or if the Investigator assesses the abnormality as an adverse event.

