1.4.3 Rationale for the NIVOLUMAB + ipilimumab clinical study

As of the 15-Feb-2013 clinical cut-off in trial CA209004, in which patients received the combination of ipilimumab with NIVOLUMAB concurrently or sequentially, of the 52 subjects evaluable for response, 21 subjects (40%) had an objective response by modified World Health Organization (mWHO) criteria²⁰⁻²¹. In an additional 2 subjects (4%) there was an unconfirmed objective response. In Cohort 1 (0.1 mg/kg nivolumab + 3 mg/kg ipilimumab), 3 out of 14 evaluable subjects had an objective response by mWHO (21%); 1 CR and 2 PRs with an additional PR by immune-related mWHO criteria (irPR).⁵⁵ In Cohort 2 (1 mg/kg nivolumab + 3 mg/kg ipilimumab), 9 out of 17 evaluable subjects had an objective response by mWHO (53%; 3 CRs (18%), 6 PRs (35%) with two additional subjects experiencing immune-related SD (irSD). In Cohort 2a (3 mg/kg nivolumab + 1 mg/kg ipilimumab), 6 out of 15 response evaluable subjects had an objective response rate by mWHO (40%; 1 CR (7%), 5 PRs (33%) with 2 additional uPRs (13%) and 2 irSDs and 1 irPR). In Cohort 3 (3 mg/kg nivolumab + 3 mg/kg ipilimumab), 3 out of 6 evaluable subjects had an objective response by mWHO (50%; 3 PRs (50%) with 1 additional irPR and 1 irSD. Preliminary analysis revealed 16 of the 52 evaluable subjects (31%) had > 80% reduction in the size of target tumor lesions by the week 12 evaluation. This is compared to < 2% for 3 mg/kg ipilimumab monotherapy based on CA184020 (N=540) and < 3% for nivolumab monotherapy based on CA209003 (N=94, 0.1-10 mg/kg. Follow-up phase II data in the randomized CA209-069 study of nivolumab + ipilimumab versus ipilimumab alone showed a 61% response rate and a 55% rate of grades 3-4 irAEs for the combination at the nivolumab dose of 1 mg/kg and ipilimumab at 3 mg/kg in the induction portion of the trial over the first 12 weeks. These data led to the FDA approval of the combination regimen for unresectable melanoma in 2015²⁰⁻²¹. The most common (reported at > 10% incidence) treatment related AEs with the combination are fatigue, rash, pruritus, diarrhea, lipase increased, pyrexia, ALT increase, AST increased, amylase increased and vitiligo. Although the preliminary data suggests an increase in adverse event frequency of nivolumab combined with ipilimumab compared to ipilimumab monotherapy or nivolumab monotherapy, there were no unexpected adverse events noted in the combination of nivolumab and ipilimumab. In addition, many of the Grade 3-4 adverse events associated with the nivolumab combined with ipilimumab were laboratory in nature, without clinical sequelae and adverse events have been manageable and reversible following intervention dose delays or with systemic steroid treatment. While the grade 3 irAE rate in that trial was 53%, the regimen was felt to be well tolerated, with a high level of clinical activity. The choice of the combination of NIVOLUMAB and ipilimumab at the chosen doses for cohort 4 of the predecessor trial MCC 15651 at Moffitt Cancer Center was based on

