4.2. Treatment Regimen

4.2.1 Toxicity management

4.2.1.1. Management:

For Grade 1 and 2 adverse events felt due to NIVOLUMAB or NIVOLUMAB with ipilimumab, symptomatic treatment is called for generally without a dose delay. For selected irAEs of grade II, especially colitis and ophthalmologic toxicity, one dose of NIVOLUMAB or NIVOLUMAB with

ipilimumab may be skipped until resolution of the toxicity to Grade 1 or less. Grade 3 irAEs that constitute dose limiting toxicity will cause treatment with NIVOLUMAB or NIVOLUMAB with ipilimumab to be discontinued permanently. For grade III irAEs that do not constitute DLT, do not require more than 2 weeks of systemic steroid treatment, and resolve within 28 days to grade I or less, with either one or no skipped doses, therapy with NIVOLUMAB or NIVOLUMAB with ipilimumab may continue at the same dose(s). There will be no dose reductions of NIVOLUMAB for an individual patient. Management of infusion reactions is defined in section 5.2.2 below.

4.2.1.2. Dose Delay:

NIVOLUMAB with ipilimumab administration should be delayed for the following:

- Any Grade ≥ 2 non-skin, drug-related adverse event, with the following exceptions:
 - Grade 2 drug-related fatigue or laboratory abnormalities do not require a treatment delay
- Any Grade 3 skin, drug-related adverse event
- Any Grade 3 drug-related laboratory abnormality, with the following exceptions for AST, ALT, total bilirubin, amylase and lipase:
 - If a subject has a baseline AST, ALT, or total bilirubin that is within normal limits, delay dosing for drug-related Grade ≥ 2 or greater toxicity
 - If a subject has baseline AST, ALT, or total bilirubin within the Grade 1 toxicity range, delay dosing for drug-related Grade ≥ 3 or greater toxicity
 - Grade 3 amylase or lipase abnormalities that are not associated with symptoms or clinical manifestations of pancreatitis do not require a dose delay. It is recommended to consult with the BMS Medical Monitor for Grade 3 amylase or lipase abnormalities.
- Any adverse event, laboratory abnormality, or intercurrent illness which, in the judgment of the investigator, warrants delaying the dose of study medication.

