5.1.6. Clinical Laboratory Tests

Samples for chemistry, hematology, and urinalysis will be taken at the times indicated on the Time and Events Schedule (Table 1) and results must be reviewed before dosing to evaluate whether or not a subject should be treated at that visit. Minimum required laboratory testing prior to each dose in all cycles: Within 72 hrs prior to re-dosing to include CBC w/ differential, LFTs, BUN or serum urea level, creatinine, Ca, Mg, Na, K, Cl, LDH, Glucose, amylase, lipase, TSH (with reflexive Free T4 and Free T3

if needed). A laboratory abnormality is considered an adverse event if it results in discontinuation from the study drugs, necessitates therapeutic medical intervention, or if the Investigator assesses the abnormality as an adverse event as described in Section 8.

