6.3.3. Safety

The safety analysis will be conducted on the Safety Population. The following safety parameters will be evaluated: adverse events, clinical laboratory tests, physical examinations, vital signs, ECOG performance status, ECGs, chest radiographs, immune safety, and immunogenicity. All safety parameters will be summarized using descriptive statistics.

- **Adverse Events**

Treatment-emergent adverse events (TEAEs) are defined as signs or symptoms that emerge during treatment or within 100 days of the last dose of study drug, including those signs and symptoms that have been absent pre-treatment or that have worsened relative to the pre-treatment assessment. Any adverse event considered related to treatment will also be considered a treatment-emergent adverse event (TEAE), regardless of the elapsed time since the last dose of study drug.

An irAE, a subset of adverse events, is defined as a clinically significant adverse event of any organ that is associated with study drug exposure, of unknown etiology, and is consistent with an immune-mediated mechanism.

All adverse events recorded during the study will be summarized using descriptive statistics. The incidence of TEAEs will be summarized by body system, preferred term, verbatim of adverse event, intensity (based on CTCAE Version 4.0 grade), and relationship to each study drug (NIVOLUMAB and/or the ipilimumab).

- **Vital Signs**

The observed vital signs at each visit and the change from baseline to each post-baseline visit will be summarized by cohort using descriptive statistics.

- **Physical Examination**

Abnormal findings in physical examination will be summarized using descriptive statistics.

- **Clinical Laboratory Tests**

Clinical laboratory test values outside the normal range and clinically significant abnormal range will be flagged in the data listing.

Laboratory data will be summarized using shift tables (baseline to notable post-baseline visit). The change from baseline will be summarized using descriptive statistics.

- **ECOG**

The data observed from ECOG performance status will be summarized appropriately.

- **Other Safety Evaluations**

The results of ECGs, chest radiographs, immune safety tests, and immunogenicity will be summarized appropriately.

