6.14 Other Safety Considerations

Any significant worsening noted during interim or final physical examinations, electrocardiograms, x-rays, and any other potential safety assessments, whether or not these procedures are required by the protocol, should also be recorded as a nonserious or serious AE, as appropriate, and reported accordingly.

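### Whether many Grade 3 laboratory values, and isolated asymptomatic Grade 4 amylase or lipase, count as adverse events rests on the sponsor-investigator's judgment, and the planned laboratory shift table does not make up for it

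*Combined protocol and SAP*

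**What the plan says.** Section 6.6 sets the rule for laboratory findings: "A laboratory abnormality is considered an adverse event if it results in discontinuation from the study drugs, necessitates therapeutic medical intervention". A third route follows, and it rests on judgment alone: "or if the Investigator assesses the abnormality as an adverse event". Section 5.1.6 repeats the rule. The general definition in the same paragraph of 6.6 is wider; it says an adverse event can be "any unfavorable and unintended sign (including an abnormal laboratory finding, for example". Section 6.14 adds a recording duty for "Any significant worsening noted during interim or final physical examinations, electrocardiograms, x-rays, and any other potential safety assessments", but ties it to no CTCAE grade.

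Section 4.2.1.2 lists, among the reasons to delay dosing, "Any Grade 3 drug-related laboratory abnormality, with the following exceptions for AST, ALT, total bilirubin, amylase and lipase". Section 4.2.1.3 says that Grade 3 drug-related laboratory abnormalities do not in general require stopping treatment, with exceptions for thrombocytopenia and liver tests. Grade 4 drug-related abnormalities do, apart from two named exceptions.

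For analysis, 6.3.3 summarises TEAE incidence by CTCAE grade, among other factors. For laboratory tests it plans flagged listings, change from baseline and shift tables: "Laboratory data will be summarized using shift tables (baseline to notable post-baseline visit". The term notable is not defined.

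On background, 1.4.3 says that "many of the Grade 3-4 adverse events associated with the nivolumab combined with ipilimumab were laboratory in nature".

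**The concern.** The primary objective (1.5) is safety and tolerability, and 1.4.3 says the trial is meant to add toxicity experience with this regimen. The TEAE table by grade is the main graded summary of that experience, and it counts only what has been recorded as an adverse event. For one important class of toxicity, recording is not automatic. The person who decides is the investigator, who is also the sponsor (Synopsis, Efficacy), in an open-label study. Two patients with the same untreated Grade 3 lipase value could be counted differently.

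A laboratory table built on the measured values would not depend on that judgment. As written, the shift table may not show the worst value, so a reader could not tell how much graded laboratory toxicity the TEAE table leaves out.

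**Working it through.** The plan gives no figure to reproduce here: no target Grade 3-4 rate and no stated share of laboratory events. The check sets the rules side by side.

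**Step 1. Routes to adverse-event status (5.1.6, 6.6).** Automatic: (a) study drug is discontinued, or (b) therapeutic intervention is needed. By judgment: (c) the investigator assesses the value as an adverse event.

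**Step 2. Drug-related laboratory values against those routes.**

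| Value | Delay (4.2.1.2) | Stop (4.2.1.3) | Automatic AE? |
|---|---|---|---|
| Grade 3 outside the named exceptions, untreated | Yes | No | No |
| Grade 3 thrombocytopenia over 7 days or with bleeding | Yes | Yes | Yes, by (a) |
| AST, ALT or bilirubin past the delay rule but below the stop thresholds, untreated | Yes | No | No |
| AST, ALT or bilirubin past the stop thresholds | Yes | Yes | Yes, by (a) |
| Grade 3 amylase or lipase, asymptomatic, untreated | Not required | No | No |
| Grade 4 in general | Superseded by stop | Yes | Yes, by (a) |
| Grade 4 electrolytes, corrected within 72 hours | Not needed for this check | Excepted | Probably, by (b) |
| Isolated Grade 4 amylase or lipase, asymptomatic, untreated | Not needed for this check | Excepted | No |

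The gap is therefore many Grade 3 values plus one Grade 4 class.

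**Step 3. How far this class matters.** Section 1.4.3 says many, without a number. Of the ten common treatment-related events it lists, four are laboratory findings: lipase, ALT, AST and amylase.

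**Step 4. Where an unrecorded value would still appear (6.3.3).**
- Listings flag values outside the normal and clinically significant ranges, not CTCAE grade, and give no proportion.
- Change from baseline describes the distribution, not the number of patients reaching Grade 3-4.
- The shift table could give that number, but only if its post-baseline column holds the worst value. An undefined visit need not, and an unscheduled test may belong to no tabulated visit.

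No planned output states the proportion of patients with any Grade 3-4 laboratory value.

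**Step 5. Size, by assumption only.** Let *r* be the true proportion of patients with any Grade 3-4 event, and *s* the share of those patients whose only such events are laboratory values never recorded as adverse events. With n = 20, recorded patients = 20 × *r* × (1 − *s*). The documents give neither *r* for this regimen nor *s*. The 55% in 1.4.3 is a Grade 3-4 immune-related event rate at other doses and serves only as an upper illustration; 30% is arbitrary.

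| *r* | *s* | 20*r*(1−*s*) | Count shown | Exact 95% CI |
|---|---|---|---|---|
| 55% | 0 | 11 | 11/20 | 31.5-76.9% |
| 55% | 25% | 8.25 | 8/20 | 19.1-63.9% |
| 55% | 50% | 5.5 | 6/20 | 11.9-54.3% |
| 30% | 0 | 6 | 6/20 | 11.9-54.3% |
| 30% | 25% | 4.5 | 4/20 | 5.7-43.7% |
| 30% | 50% | 3 | 3/20 | 3.2-37.9% |

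Half-patients are shown as one of the two neighbouring integers. At *s* = 0 nothing is lost; at larger *s* the loss is material. The documents do not say where *s* lies.

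**The case against.** The strongest reply is that the plan already brings these values in. The investigator clause covers any grade, the general definition names abnormal laboratory findings, and 6.14 requires significant worsening to be recorded. Section 4.2.1.2 lets dosing resume when the drug-related adverse events have resolved and then lists AST, ALT and bilirubin exceptions, so it treats delay-causing abnormalities as adverse events. Most drug-related Grade 4 values qualify automatically because they stop treatment. Listings, shift tables and change from baseline are produced whatever the adverse-event status.

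Most of this stands, and it limits the point. A reader might infer that an untreated or dose-delaying laboratory value is excluded from the adverse events by rule. The documents do not support that: it is left to judgment, not excluded. Nor does the wording of the TEAE definition in 6.3.3 (signs or symptoms) exclude laboratory findings, since 6.6 counts an abnormal finding as a sign. The undefined shift-table visit removes nothing from the adverse-event tables; it weakens only the backup.

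What the reply does not supply is a rule. The wider definition says what an adverse event can be, 6.14 does not define significant, and the delay text in 4.2.1.2 does not match the triggers in 5.1.6 and 6.6. Asymptomatic Grade 3 amylase or lipase requires no delay, so even reading delay as evidence of adverse-event status leaves that group to judgment.

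**Conclusion.** The point holds as a limited one. The graded TEAE table may under-capture laboratory toxicity, because many Grade 3 values and isolated asymptomatic Grade 4 amylase or lipase are adverse events only if the sponsor-investigator says so, and no planned laboratory summary reliably shows the worst grade. The effect cannot be computed from the documents and is zero if all such values are recorded. The table in the working rests on assumed values of *r* and *s*.

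Three stronger conclusions are tempting and unsupported:
- That a primary Grade 3-4 rate is biased. No such rate is named: the primary objective is assessed descriptively, and section 2.2, headed as the primary endpoint, gives time to relapse.
- That much of the regimen's toxicity is omitted. Section 1.4.3 gives no share, and refers to events, not patients.
- That comparison with the 41%, 53% and 55% rates is spoiled. The 41% is ipilimumab alone at 10 mg/kg (1.4). The 55% is for nivolumab 1 mg/kg plus ipilimumab 3 mg/kg, and the 53% is cited in choosing the predecessor trial's cohort 4, which used that schedule (1.4.3). The present regimen rests on 17 of 20 patients continuing past week 12. The plan proposes no comparison with the three rates, and those studies' recording rules are not in the documents.

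**What to change.** In 6.3.3, run the shift table from baseline to the worst post-baseline CTCAE grade at any scheduled or unscheduled test, in place of the notable visit. Beside the Grade 3-4 TEAE table, report the proportion of the Safety Population with any Grade 3-4 laboratory value, whether or not it was recorded as an adverse event. Cross-classifying the two by patient would show the under-capture directly instead of leaving it to assumption. This table changes neither adverse-event status nor dose-limiting toxicity (DLT) counts.

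Separately, reconcile the rule in 5.1.6 and 6.6 with 4.2.1.2, and state whether dose-delaying and Grade 3-4 laboratory values are to be recorded as adverse events. Simply adding a delayed dose as a trigger would be weak, because it misses asymptomatic amylase and lipase. Any change to the rule could also alter DLT counts and the stopping rule, since a DLT must be an adverse event (4.2.4.1, 4.2.5); the sponsor should say how that is handled.

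The table uses data already collected. It costs one extra table, and the displayed toxicity may look less favourable.

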6.7. Serious Adverse Events

A **serious adverse event (SAE)** is any untoward medical occurrence that:

- results in death

- is life-threatening (defined as an event in which the subject was at risk of death at the time of the event; it does not refer to an event that hypothetically might have caused death if it were more severe)
- requires inpatient hospitalization or causes prolongation of existing hospitalization (see “note” below for exceptions)
- results in persistent or significant disability/incapacity
- is a congenital anomaly/birth defect
- Suspected transmission of an infectious agent (eg, any organism, virus or infectious particle, pathogenic or non-pathogenic) via the study drug is an SAE.
- is an important medical event (defined as a medical event(s) that may not be immediately life-threatening or result in death or hospitalization but, based upon appropriate medical and scientific judgment, may jeopardize the subject or may require intervention [eg, medical, surgical] to prevent one of the other serious outcomes listed in the definition above.) Examples of such events include, but are not limited to, intensive treatment in an emergency room or at home for allergic bronchospasm; blood dyscrasias or convulsions that do not result in hospitalization.)
- Although overdose and cancer are not always serious by regulatory definition, these events should be reported on an SAE form and sent to BMS in an expedited manner. An overdose is defined as the accidental or intentional ingestion or infusion of any dose of a product that is considered both excessive and medically important.

NOTE: The following hospitalizations are not considered SAEs in BMS clinical studies:

- a visit to the emergency room or other hospital department for less than 24 hours that does not result in admission (unless considered an “important medical event” or a life-threatening event)
- elective surgery, planned before signing consent
- admissions as per protocol for a planned medical/surgical procedure
- routine health assessment requiring admission for baseline/trending of health status (eg, routine colonoscopy)
- medical/surgical admission for purpose other than remedying ill health state and was planned prior to entry into the study. Appropriate documentation is required in these cases
- admission encountered for another life circumstance that carries no bearing on health status and requires no medical/surgical intervention (eg, lack of housing, economic inadequacy, care-giver respite, family circumstances, administrative).

Note that all pregnancies, regardless of outcome, must be reported to the sponsor-investigator on a Pregnancy Surveillance Form, not an SAE form. All pregnancies must be reported and followed to outcome, including pregnancies that occur in the female partner of a male study subject. **See Section 8.4 for instructions on reporting pregnancies.**

Nonserious Adverse Events

A non-serious adverse event is an AE not classified as serious.

6.7.1. Assignment of Adverse Event Intensity and Relationship to Investigational Product

Describe how adverse events (AEs and SAEs) will be graded, for example:

For oncology studies:

Version 4.0 of the NCI Common Terminology Criteria for Adverse Events (CTCAE) will be utilized for AE reporting. Version 4.0 of the CTCAE is identified and located on the CTEP website at http://ctep.cancer.gov/protocolDevelopment/electronic_applications/ctc.htm. All appropriate treatment areas should have access to a copy of Version 4.0 of CTCAE.

The following categories and definitions of causal relationship to investigational product as determined by a physician should be used:

- **Related:** There is a reasonable causal relationship to investigational product administration and the adverse event.
- **Not Related:** There is not a reasonable causal relationship to investigational product administration and the adverse event.

The expression “reasonable causal relationship” is meant to convey in general that there are facts (eg, evidence such as de-challenge/re-challenge) or other arguments to suggest a positive causal relationship.

6.7.2. Collection and Reporting

Adverse events can be spontaneously reported or elicited during open-ended questioning, examination, or evaluation of a subject. (In order to prevent reporting bias, subjects should not be questioned regarding the specific occurrence of one or more AEs.)

If known, the diagnosis of the underlying illness or disorder should be recorded, rather than its individual symptoms. The following information should be captured for all AEs: onset, duration, intensity, seriousness, relationship to investigational product, action taken, and treatment required. If treatment for the AE was administered, it should be recorded in the medical record.

The sponsor-investigator shall supply the ethics Committee with any additional requested information, notably for reported deaths of subjects.

